5.5.1 Acceptable Concomitant medications

All treatments that the investigator considers necessary for a subject's welfare may be administered at the discretion of the investigator in keeping with the community standards of medical care. All concomitant medication will be recorded on the electronic case report form (eCRF) including all prescription, over-the-counter (OTC), herbal supplements, and IV medications and fluids. If changes occur during the trial period, documentation of drug dosage, frequency, route, and date may also be included on the eCRF.

All concomitant medications received within 28 days before the first dose of trial treatment and 30 days after the last dose of trial treatment should be recorded. Concomitant medications administered after 30 days after the last dose of trial treatment should be recorded for SAEs and events of clinical interest (ECIs) as defined in Section 7.2.

5.5.2 Prohibited Concomitant Medications

Subjects are prohibited from receiving the following therapies during the Screening and Treatment Phase (including retreatment for post-CR relapse) of this trial:

- Antineoplastic systemic chemotherapy or biological therapy
- Immunotherapy not specified in this protocol

- Chemotherapy not specified in this protocol
- Investigational agents other than pembrolizumab
- Radiation therapy
 - Note: Radiation therapy to a symptomatic solitary lesion or to the brain may be allowed after consultation with Sponsor (except during screening).
- Live vaccines within 30 days prior to the first dose of trial treatment and while participating in the trial. Examples of live vaccines include, but are not limited to, the following: measles, mumps, rubella, varicella/zoster, yellow fever, intranasal influenza, rabies, Bacillus Calmette–Guérin, and typhoid vaccine.
- Glucocorticoids for any purpose other than to modulate symptoms from an event of suspected immunologic etiology or from symptomatic brain metastasis(es) (also during whole brain radiation therapy). The use of physiologic doses of corticosteroids may be approved after consultation with the Sponsor.
 - Note: Inhaled steroids are allowed for management of asthma.
 - Note: Use of prophylactic corticosteroids to avoid allergic reactions (e.g., to IV contrast dye) is permitted.

Subjects who, in the assessment by the investigator, require the use of any of the aforementioned treatments for clinical management should be removed from the trial. Subjects may receive other medications that the investigator deems to be medically necessary.

The Exclusion Criteria describes other medications which are prohibited in this trial.

There are no prohibited therapies during the Post-Treatment Follow-up phase.

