5.5 Concomitant Medications/Vaccinations (Allowed & Prohibited)

Medications or vaccinations specifically prohibited in the exclusion criteria are not allowed during the ongoing trial. If there is a clinical indication for any medication or vaccination specifically prohibited during the trial, discontinuation from trial therapy or vaccination may be required. The investigator should discuss any questions regarding this with the Sponsor Clinical Director. The final decision on any supportive therapy or vaccination rests with the investigator and/or the subject's primary physician. However, the decision to continue the subject on trial therapy or vaccination schedule requires the mutual agreement of the investigator, the Sponsor and the subject.

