5.7.3 Use in Pregnancy

If a subject inadvertently becomes pregnant while on treatment with pembrolizumab, the subject will immediately be removed from the study. The site will contact the subject at least monthly and document the subject's status until the pregnancy has been completed or terminated. The outcome of the pregnancy will be reported to the Sponsor without delay and within 24 hours if the outcome is a serious adverse experience (e.g., death, abortion, congenital anomaly, or other disabling or life-threatening complication to the mother or newborn). The study investigator will make every effort to obtain permission to follow the outcome of the pregnancy and report the condition of the fetus or newborn to the Sponsor.

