5.8 Subject Withdrawal/Discontinuation Criteria

Subjects may withdraw consent at any time for any reason or discontinued from study therapy at the discretion of the investigator should any untoward effect occur. In addition, a subject may be withdrawn by the investigator or the Sponsor if enrollment into the trial is inappropriate, the trial plan is violated, or for administrative and/or other safety reasons. Specific details regarding discontinuation or withdrawal procedures; including specific details regarding withdrawal from Future Biomedical Research, are provided in Section 7.1.4 – Other Procedures.

In this trial, a subject may discontinue from treatment but continue to participate in the regularly scheduled activities, as long as the subject does not withdraw consent.

A subject must be discontinued from the trial for any of the following reasons:

- The subject or legal representative (such as a parent or legal guardian) withdraws consent.
- The subject is lost to follow-up.

A subject must be discontinued from treatment (but may continue to be monitored in the trial) for any of the following reasons:

- The subject or legal representative (such as a parent or legal guardian) withdraws consent for treatment.
- Confirmed radiographic disease progression.

Note: For unconfirmed radiographic disease progression, please see Section 7.1.2.6.2.

- Unacceptable adverse experiences as described in Section 5.2.1.2
- Intercurrent illness that prevents further administration of treatment
- Investigator's decision to withdraw subject
- The subject has a confirmed positive serum pregnancy test

- Noncompliance with trial treatment or procedure requirements
- Completed 35 treatments (approximately 2 years) with pembrolizumab

Note: 35 treatments (approximately 2 years) are calculated from the first dose. Subjects who stop pembrolizumab after receiving 35 treatments may be eligible for retreatment if they progress after stopping study treatment if they meet the requirements detailed in Section 7.1.5.2.1. Subjects may be retreated in the Second Course Phase with up to 17 (approximately 1 year) of additional trial treatments.

- Administrative reasons

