7.1.1.6 Subsequent Anti-Cancer therapy Status

All new anti-cancer therapy initiated after the study start must be recorded in the subsequent anti-cancer therapy eCRF page. If a subject initiates another anti-cancer therapy while receiving pembrolizumab, pembrolizumab must be discontinued and subject will move into Survival Follow-up Phase; if a subject initiates a new anti-cancer therapy within 30 days after the last dose of the trial treatment, the 30 day Safety Follow-up visit must occur before the first dose of the new therapy.

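### Section 5.5.2 removes subjects who need a prohibited therapy from the trial, while the follow-up sections keep them in it; taken literally it loses deaths and SAEs and can overstate OS

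*Combined protocol and SAP*

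**What the plan says.** Section 5.5.2 lists therapies prohibited during screening and treatment, including retreatment: other antineoplastic therapy, other investigational agents, radiation, live vaccines, and glucocorticoids outside stated uses. It then directs that subjects who "require the use of any of the aforementioned treatments for clinical management should be removed from the trial". There are exceptions. One is that "Radiation therapy to a symptomatic solitary lesion or to the brain may be allowed after consultation with Sponsor", though not during screening; several steroid uses are also allowed. The section closes: "There are no prohibited therapies during the Post-Treatment Follow-up phase".

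Other parts of the protocol treat the same subjects differently:

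- **Trial Summary (1.0), follow-up period:** every subject is telephoned for OS until she dies, withdraws consent or the study ends.
- **5.5, the parent section:** if a prohibited medication is indicated, "discontinuation from trial therapy or vaccination may be required".
- **5.8:** "a subject may discontinue from treatment but continue to participate in the regularly scheduled activities", provided consent is not withdrawn. Only two reasons make leaving the trial mandatory: withdrawn consent and loss to follow-up.
- **7.1.1.6:** if other anti-cancer therapy starts during pembrolizumab, "pembrolizumab must be discontinued and subject will move into Survival Follow-up Phase".
- **7.1.5.3.4:** survival contact continues about every 12 weeks after confirmed progression or new anti-cancer therapy.

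The pregnancy text has a similar conflict. Section 5.7.3 says "the subject will immediately be removed from the study", while 5.8 lists a confirmed positive pregnancy test as a reason to stop treatment, with monitoring in the trial still possible.

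**The concern.** For a subject who starts chemotherapy while on pembrolizumab, 5.5.2 and 7.1.1.6 give opposite instructions about whether she is still in the trial. Two sites could each follow the protocol and collect different data.

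OS is a secondary objective in every cohort and subgroup (3.2), and the sSAP (Table 3) censors it at the last known alive date. A death after removal would therefore never be counted. If the need for a prohibited therapy signals deterioration, that censoring is informative and pushes the Kaplan-Meier curve upward. Safety data are exposed as well: a subject out of the trial is no longer asked about new SAEs. Contacts that were never made cannot be restored by analysis, so the remedy belongs in the protocol.

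**Working it through.** **Step 1. What literal removal adds, endpoint by endpoint.**

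| Endpoint | Rule in the plan | Added effect of removal |
|---|---|---|
| OS | Censored at last known alive date (sSAP Table 3) | Later deaths lost |
| PFS, subject starts other anti-cancer therapy | Imaging stops (7.1.2.6.2, 7.1.2.6.4); with no PD or death, censored at the last assessment before that therapy (sSAP Table 2) | Only deaths after the new therapy, which are events on a literal reading of Table 2 |
| PFS, subject needs a therapy that is not anti-cancer | Imaging would otherwise continue | PD or death lost |
| DOR | With no PD or death, censored at the last adequate assessment before new anti-cancer therapy (sSAP Table 1) | None in that case |
| ORR (primary) | Confirmed response required (sSAP 3.4.1); missing counts as non-response (sSAP 3.6.1) | A lost confirmation scan can only lower it |
| SAEs | 90 days after treatment, or 30 days if new anti-cancer therapy starts, whichever is earlier (7.2.3.1) | New events in that window can be missed; 7.1.4.1 follows only AEs present at withdrawal |

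**Step 2. Size of the OS effect.** The documents give no removal rate and no OS planning figure, so there is nothing of the plan's own to reproduce. Every rate below is an assumption.

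Inputs for median OS, both historical figures from 4.1.1.1: 10 months (lower end of 10 to 12 months, single agents in platinum-resistant disease) and 393 days ÷ 30.44 = 12.9 months (TFI of 3 to 12 months).

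Model: death hazard h before removal, constant removal hazard r, death hazard HR·h after removal.

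- Fraction removed before death: f = r/(h + r), so r = h·f/(1 − f).
- True survival: S(t) = exp(−(h+r)t) + r·[exp(−HR·h·t) − exp(−(h+r)t)] / (h + r − HR·h).
- Kaplan-Meier median when removal is treated as censoring: ln 2 / h.
- h is chosen so that S at the true median is 0.5.

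Example, true median 10 months, f = 0.10, HR = 3: h = 0.06608 and r = 0.06608 × 0.10/0.90 = 0.00734. Then S(10) = exp(−0.734) + 0.00734 × [exp(−1.982) − exp(−0.734)]/(0.0734 − 0.1982) = 0.480 + 0.020 = 0.500. The censored median is 0.6931/0.06608 = 10.49, an overstatement of 0.49 months.

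Overstatement of median OS in months (true median 10; true median 12.9):

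| Removed | HR 1 | HR 2 | HR 3 |
|---|---|---|---|
| 5% | 0; 0 | 0.14; 0.19 | 0.24; 0.31 |
| 10% | 0; 0 | 0.30; 0.38 | 0.49; 0.63 |
| 20% | 0; 0 | 0.64; 0.83 | 1.05; 1.35 |

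At 10% removed and HR 3, 12-month OS is overstated by 45.2 − 43.3 = 1.9 points (true median 10) or 54.1 − 52.6 = 1.5 points (true median 12.9).

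**Step 3. Sensitivity to timing.** Suppose instead that a fraction f has the removal event uniformly over months 1 to 6, and that the hazard without it is h = ln 2/12. True survival is (1 − f)·exp(−h·t) plus f times the average, over removal times u, of exp(−h·u − HR·h·(t − u)) for t > u, or exp(−h·t) for t ≤ u. The censored median is 12.0. The true median is 11.4 (HR 2) or 11.0 (HR 3) with f = 0.10, and 11.1 or 10.5 with f = 0.15. Early removal therefore gives a larger bias at the same fraction: about 0.6 to 1.0 months at 10% and 0.9 to 1.5 at 15%. It is still zero at HR 1.

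**The case against.** The strongest reply is that one loose sentence is outweighed by the rest of the protocol. The Trial Summary promises OS contact for all subjects. Section 7.1.5.4 and footnote b of the flow chart in 6.1 let the sponsor ask for survival status on any participant without a scheduled contact. The parent section speaks only of stopping trial therapy. The closing line of 5.5.2 on post-treatment follow-up also fits a subject who leaves treatment for follow-up. This shows what the sponsor probably meant. It does not remove the contrary instruction, and the sponsor's sweep is optional and covers participants, which a removed subject arguably is not.

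Other points stand and limit the concern. Section 5.8 allows discretionary withdrawal if the trial plan is violated, so its two mandatory reasons are not a closed list. Section 7.1.1.6 covers only anti-cancer therapy. Section 7.2.3.1 still requires an SAE judged related to be reported whenever it comes to the investigator's attention. In pregnancy, 5.7.3 itself requires at least monthly contact. OS and PFS are descriptive secondary endpoints with no hypothesis test.

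A reader might infer more: that 5.5.2 strips the trial of its sickest subjects and so overstates both OS and PFS. The documents do not support that. The rule has exceptions, ends with the treatment phase, and also covers live vaccines, which say nothing about prognosis. OS bias is zero if prognosis after removal is unchanged. Much of the PFS loss would arise anyway from the plan's own imaging stop and censoring rule.

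**Conclusion.** The contradiction is real and should be resolved. Following 5.5.2 literally loses later deaths and possibly new SAEs. It can overstate OS, on condition that removed subjects do worse than those who remain. For PFS the added loss is confined to the two situations shown in the first table, and it was not modelled. Primary ORR cannot be inflated by it.

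The size cannot be known from the documents. The range of 0 to about 1.35 months in median OS rests on assumed removal of 5 to 20% at a constant rate, a later hazard 1 to 3 times higher, exponential survival, and true medians of 10 to 12.9 months. Removal concentrated in the first months would give more; fewer removals or an unchanged prognosis would give less or nothing. Because the affected efficacy endpoints are secondary and descriptive, this is a moderate inconsistency and not a threat to the primary analysis.

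**What to change.** In 5.5.2, replace the removal clause with wording that, unless consent is withdrawn, the subject remains in the trial for:

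- SAE collection under 7.2.3.1;
- survival follow-up as in the Trial Summary and 7.1.5.3.4;
- disease-status imaging until progression or new anti-cancer therapy, as 7.1.2.6.4 and 7.1.5.3.3 already provide.

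Reconcile the removal wording in 5.7.3 with the pregnancy entry in 5.8. Whether and when study treatment stops in each situation is for the sponsor to reconcile across 5.5, 5.5.2, 5.8 and 7.1.1.6; no clinical rule is proposed here.

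The cost is about one sentence in each of two sections. The follow-up uses visits and calls already in the flow chart.

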5.6 Rescue Medications & Supportive Care

5.6.1 Supportive Care Guidelines

Subjects should receive appropriate supportive care measures as deemed necessary by the treating investigator. Suggested supportive care measures for the management of AEs with potential immunologic etiology are outlined along with the dose modification guidelines in [Table 3](#). Where appropriate, these guidelines include the use of oral or IV treatment with corticosteroids, as well as additional anti-inflammatory agents if symptoms do not improve with administration of corticosteroids. Note that several courses of steroid tapering may be necessary as symptoms may worsen when the steroid dose is decreased. For each disorder, attempts should be made to rule out other causes such as metastatic disease or bacterial or viral infection, which might require additional supportive care. The treatment guidelines are intended to be applied when the investigator determines the events to be related to pembrolizumab.

Note: If after the evaluation of the event, it is determined not to be related to pembrolizumab, the investigator does not need to follow the treatment guidance.

It may be necessary to perform conditional procedures such as bronchoscopy, endoscopy, or skin photography as part of evaluation of the event.

5.7 Diet/Activity/Other Considerations

5.7.1 Diet

Subjects should maintain a normal diet unless modification is required to manage an AE such as diarrhea, nausea or vomiting.

5.7.2 Contraception

Pembrolizumab may have adverse effects on a fetus in utero. Furthermore, it is not known if pembrolizumab has transient adverse effects on the composition of sperm.

Female subjects will be considered to be of non-reproductive potential if they are either:

- 1) postmenopausal (defined as at least 12 months with no menses without an alternative medical cause; in women <45 years of age a high follicle-stimulating hormone (FSH) level in the postmenopausal range may be used to confirm a post-menopausal state in women not using hormonal contraception or hormonal replacement therapy. In the absence of 12 months of amenorrhea, a single FSH measurement is insufficient.);

OR

- 2) have had a hysterectomy and/or bilateral oophorectomy, bilateral salpingectomy or bilateral tubal ligation/occlusion, at least 6 weeks prior to screening;

OR

- 3) has a congenital or acquired condition that prevents childbearing.

Female and male subjects of reproductive potential must agree to avoid becoming pregnant or impregnating a partner, respectively, while receiving study drug and for 120 days after the last dose of study drug by complying with one of the following:

- 1) practice abstinence† from heterosexual activity;

OR

- 2) use (or have their partner use) acceptable contraception during heterosexual activity.

Acceptable methods of contraception are‡:

Single method (one of the following is acceptable):

- intrauterine device (IUD)
- vasectomy of a female subject's male partner
- contraceptive rod implanted into the skin

Combination method (requires use of 2 of the following):

- diaphragm with spermicide (cannot be used in conjunction with cervical cap/spermicide)
- cervical cap with spermicide (nulliparous women only)
- contraceptive sponge (nulliparous women only)

- male condom or female condom (cannot be used together)
- hormonal contraceptive: oral contraceptive pill (estrogen/progestin pill or progestin-only pill), contraceptive skin patch, vaginal contraceptive ring, or subcutaneous contraceptive injection

† Abstinence (relative to heterosexual activity) can be used as the sole method of contraception if it is consistently employed as the subject's preferred and usual lifestyle and if considered acceptable by local regulatory agencies and ERCs/IRBs. Periodic abstinence (e.g., calendar, ovulation, sympto-thermal, post-ovulation methods, etc.) and withdrawal are not acceptable methods of contraception.

‡ If a contraceptive method listed above is restricted by local regulations/guidelines, then it does not qualify as an acceptable method of contraception for subjects participating in this country/region.

Subjects should be informed that taking the study medication may involve unknown risks to the fetus (unborn baby) if pregnancy were to occur during the study. In order to participate in the study, they must adhere to the contraception requirement (described above) from the day of study medication initiation (or 14 days prior to the initiation of study medication for oral contraception) throughout the study period up to 120 days after the last dose of trial therapy. If there is any question that a subject of childbearing potential will not reliably comply with the requirements for contraception, that subject should not be entered into the study.

Below are the required contraception's for countries where the health authority requests compliance with the Clinical Trial Facilitation Group Guidance:

Subjects should use birth control methods that can achieve a failure rate of less than 1% per year when used consistently and correctly and are considered as highly effective birth control methods. Such methods include:

- Combined (estrogen and progestogen containing) hormonal contraception associated with inhibition of ovulation:
 - Oral
 - Intravaginal
 - Transdermal
- Progestogen-only hormonal contraception associated with inhibition of ovulation:
 - Oral
 - Injectable
 - Implantable
 - IUD
 - Intrauterine hormone-releasing system
 - Bilateral tubal occlusion
 - Vasectomized partner
 - Sexual abstinence

5.7.3 Use in Pregnancy

If a subject inadvertently becomes pregnant while on treatment with pembrolizumab, the subject will immediately be removed from the study. The site will contact the subject at least monthly and document the subject's status until the pregnancy has been completed or terminated. The outcome of the pregnancy will be reported to the Sponsor without delay and within 24 hours if the outcome is a serious adverse experience (e.g., death, abortion, congenital anomaly, or other disabling or life-threatening complication to the mother or newborn). The study investigator will make every effort to obtain permission to follow the outcome of the pregnancy and report the condition of the fetus or newborn to the Sponsor.

5.7.4 Use in Nursing Women

It is unknown whether pembrolizumab is excreted in human milk. Since many drugs are excreted in human milk, and because of the potential for serious adverse reactions in the nursing infant, subjects who are breastfeeding are not eligible for enrollment.

5.8 Subject Withdrawal/Discontinuation Criteria

Subjects may withdraw consent at any time for any reason or discontinued from study therapy at the discretion of the investigator should any untoward effect occur. In addition, a subject may be withdrawn by the investigator or the Sponsor if enrollment into the trial is inappropriate, the trial plan is violated, or for administrative and/or other safety reasons. Specific details regarding discontinuation or withdrawal procedures; including specific details regarding withdrawal from Future Biomedical Research, are provided in Section 7.1.4 – Other Procedures.

In this trial, a subject may discontinue from treatment but continue to participate in the regularly scheduled activities, as long as the subject does not withdraw consent.

A subject must be discontinued from the trial for any of the following reasons:

- The subject or legal representative (such as a parent or legal guardian) withdraws consent.
- The subject is lost to follow-up.

A subject must be discontinued from treatment (but may continue to be monitored in the trial) for any of the following reasons:

- The subject or legal representative (such as a parent or legal guardian) withdraws consent for treatment.
- Confirmed radiographic disease progression.

Note: For unconfirmed radiographic disease progression, please see Section 7.1.2.6.2.

- Unacceptable adverse experiences as described in Section 5.2.1.2
- Intercurrent illness that prevents further administration of treatment
- Investigator's decision to withdraw subject
- The subject has a confirmed positive serum pregnancy test

- Noncompliance with trial treatment or procedure requirements
- Completed 35 treatments (approximately 2 years) with pembrolizumab

Note: 35 treatments (approximately 2 years) are calculated from the first dose. Subjects who stop pembrolizumab after receiving 35 treatments may be eligible for retreatment if they progress after stopping study treatment if they meet the requirements detailed in Section 7.1.5.2.1. Subjects may be retreated in the Second Course Phase with up to 17 (approximately 1 year) of additional trial treatments.

- Administrative reasons

The End of Treatment and Follow-up visit procedures are listed in Section 6 (Trial Flow Chart) and Section 7.1.5 (Visit Requirements). After the end of treatment, each subject will be followed for 30 days for AE monitoring (SAEs will be collected for 90 days after the end of treatment or 30 days after the end of treatment if the subject initiates new anti-cancer therapy, whichever is earlier, as described in Section 7.2.3.1). Subjects who discontinue for reasons other than progressive disease will have post-treatment follow-up for disease status until disease progression, initiating a non-study cancer treatment, withdrawing consent or becoming lost to follow-up. After documented disease progression, each subject will be followed by telephone for overall survival until death, withdrawal of consent, or the end of the study, whichever occurs first.

